3.5 Rationale for this study

Despite the treatment advances in the treatment of brain metastases, prognosis remains poor and there are no specific biomarkers available to predict response of brain metastases to available therapies. FLT-PET has been used as an imaging biomarker in patients with brain tumors to predict response to anti-angiogenic therapy. This was achieved by performing serial FLT PET imaging [21].

Following WBRT, patients often progress clinically or on MR imaging. Furthermore, radiation necrosis, a well-known phenomenon can complicate cranial radiotherapy and patients could decline quickly, often not because of disease progression in the brain, but as a result of mass effect and edema caused by necrosis [22]. Also, there is a suggestion that targeting VEGF can reduce radionecrosis by decreasing capillary leakage and the associated brain edema [23, 24] as well as potentiate the antitumor effects of external beam radiotherapy [17]. A small randomized controlled trial has shown benefit of antiangiogenic therapy for established radionecrosis [Grommes *et al. Proceedings of AAN*; 2010]. This however has not been confirmed in a well-powered randomized trial. As an antiangiogenic agent, sorafenib could potentially reduce complications of cranial radiation such as increased edema and radionecrosis. We therefore aim to explore the effect of sorafenib on the development of suspected or proven radionecrosis.

Our hypothesis is that FLT-PET will be a more accurate non-invasive biomarker than MRI in patients with metastatic breast cancer with metastases to the brain treated with WBRT with or without sorafenib. This is expected based on the higher specificity of FLT for viable residual disease. The hypothesis will be tested by having patients undergo

FLT PET and MR at baseline, FLT PET within 7-10 days after radiotherapy (for early response assessment) and again dual imaging at 10-12 weeks post WBRT.

3.6 Analysis of surgical specimen

Comparing FLT PET findings with tissue analysis will enable us to determine if imaging results are concordant with histological findings and thus allow for confirmation of this hypothesis. In this manner, we propose to generate a bridge between tissue analysis and FLT-PET brain imaging studies. For patients needing to undergo craniotomy for resection of a brain metastasis after WBRT, tissue findings (radionecrosis versus viable tumor) will be correlated with radiologic assessment in an exploratory manner.

4.1 OVERVIEW OF STUDY DESIGN/INTERVENTION

4.2 Design

We will perform a pilot study of serial FLT-PET imaging of the brain at baseline (< 4 weeks prior to initiation of WBRT), up to 7-10 days post-WBRT and 10-12 weeks after WBRT in patients with metastatic breast cancer to the brain (N=20) treated with WBRT with or without sorafenib. We will assess and quantify the radiographic response of WBRT, measure the impact of sorafenib on radiographic response, determine early treatment response and distinguish tumor progression from radionecrosis.

This exploratory study will include two cohorts with 10 patients each. Cohort 1 will include the first ten patients treated with WBRT concomitantly with sorafenib (on a separate phase I trial). Cohort 2 will include patients treated with standard WBRT alone. Patients in both these cohorts will also be assessed with standard non-invasive MRI in addition to [¹⁸F] FLT PET at baseline (< 4 weeks of WBRT) and 10-12 weeks after completion of WBRT. Patients will later be followed with MR imaging of the brain every 3 months (+/- 7 days) during the first year, every 6 months (+/- 7 days) thereafter until CNS progression or death. These follow-up scan time-points are considered standard of care. Of note, patients with a negative FLT-PET at baseline will be taken off study.

Tissue from patients who have medical indication for craniotomy and have a signed consent will be assessed for radiation necrosis and these findings will be correlated with the imaging studies and treatment (Section 9.3).

4.3 Intervention

All patients will be imaged using FLT-PET scans at baseline (within 4 weeks of initiation of WBRT), 7-10 days after completion of WBRT and then 10-12 weeks after WBRT.

Patients will also be evaluated with MRI imaging at baseline and then 10-12 weeks after WBRT.

Patients will be followed with MRI every 3 months (+/- 7 days) for the first year and then every 6 months (+/- 7 days) thereafter which is the standard of care.

5.0 THERAPEUTIC/DIAGNOSTIC AGENTS

[¹⁸F] FLT

The radiotracer, ¹⁸F-FLT, has been synthesized by the MSKCC cyclotron facility for approximately two years, and has been used in humans in this and other institutions in this country and Europe. The primary source of the FLT will be the MSKCC cyclotron facility; however, alternative commercial sources are available to ensure consistent supply of FLT. If a commercial supplier of FLT is used for a particular study (such as Cardinal Health), the supplier will be required to meet all of the acceptance criteria outlined in the FDA-approved MSKCC FLT IND (#104742) prior to administration. The FLT will be tested to ensure radiochemical purity is > 95% and for pyrogenicity.

FLT will be administered as part of an FDA-approved IND application, based on dosimetry estimates (see section 8.2). Whereas the primary source of the FLT will be the MSKCC cyclotron facility, alternative commercial sources are available and used provided that supplier meet all of the acceptance criteria outlined in the FDA-approved MSKCC FLT IND (#104742) prior to administration.

6.1 CRITERIA FOR SUBJECT ELIGIBILITY

6.2 Subject Inclusion Criteria

- Histologically-confirmed (confirmation done at MSKCC) metastatic adenocarcinoma of the breast
- Radiologic evidence of new and/or progressive brain metastases (≥ 10 mm in longest dimension) by MRI imaging of the Brain
- Planned WBRT based on number (≥ 3 lesions) and/or size (≥ 1 cm) of brain metastases.
- Age ≥ 18 years; males and females
- Patients who require additional clinically indicated stereotactic radiosurgery (SRS) in addition to WBRT will also be eligible.
- Life expectancy of >12 weeks.
- Karnofsky Performance Status (KPS) $\geq 70\%$.
- Creatinine ≤ 2.0 times the upper limit of normal.
- Women of childbearing potential must have a negative serum pregnancy test performed within 7 days prior to enrollment, must be non-lactating and must agree to use adequate contraception prior to enrollment and for the duration of study participation.
- No limit to prior therapies with last anti-cancer treatment ≥ 2 weeks from initiation of WBRT. Please note: there is no washout period required for trastuzumab, pertuzumab for patients who have developed new parenchymal brain metastases while on these agents.

6.3 Subject Exclusion Criteria

- Leptomeningeal metastases. Please note: leptomeningeal metastases may be allowed if it is limited to cranial metastasis (MRI spine should be completed, within 4 weeks of enrollment, to show that no other leptomeningeal metastases is present) and is not the only metastasis present in the brain.
- Concurrent administration of lapatinib or other tyrosine kinase inhibitors other than sorafenib
- Craniotomy or any other major surgery, open biopsy, or significant traumatic injury within 4 weeks of randomization.
- Concurrent anti-cancer therapy (chemotherapy, hormonal therapy, radiation therapy, surgery, immunotherapy, biologic therapy, or tumor embolization) other than sorafenib, and protocol-specified whole-brain radiotherapy.
- Use of any investigational drug within 30 days or 5 half-lives, whichever is longer, preceding enrollment.
- Inability to comply with protocol and /or not willing or not available for follow-up assessments.

- Any condition which in the investigator's opinion makes the patient unsuitable for the study participation.
- Patient is incontinent of urine or stool (which would make them unable to tolerate lying still for 60 minutes).
- Claustrophobia
- Known allergic reaction to Gd-DTPA
- Renal insufficiency with recent (<3 month old) creatinine >2.0
- Any contraindication to MRI (e.g., pacemaker, aneurysm clip, tissue expander)

7.1 RECRUITMENT PLAN

Recruitment of patients will be through the participating investigators from the Breast Service and referrals from staff physicians at Memorial Hospital. Patients could be identified through clinic lists. A detailed description of the study procedures will be provided to each referring physician and a simpler version to each patient by the principal investigator or one of the investigators of this research proposal.

Patients will be required to sign a statement of informed consent that meets the requirements of the code of Federal Regulations (Federal register Vol.46, No. 17, Jan.27, 1981, part 50) and the IRB of this center. The medical record will include a statement that written informed consent was obtained (and document in the record the date written consent was obtained before) and the patient is enrolled in the study.

All patients who meet the above inclusion and exclusion criteria will be invited to participate in the study by their primary oncologist. Study Investigators will invite men and women and all minorities on an equal basis as they present to their oncologist during routine cancer care visits. Consenting professionals will meet the patients and obtain informed consent.

It is important to note that the first ten patients on cohort 1 on this protocol would have agreed to and signed informed consent for a separate but simultaneous phase I trial of sorafenib with WBRT. This protocol is currently undergoing the IRB review process simultaneously.

8.0 PRETREATMENT EVALUATION

- MR Brain will be obtained within 4 weeks prior to initiation of WBRT to ensure evidence of new/progressive brain metastases. MR imaging will include images before and after the administration of gadolinium-diethylenetriamine - pentaacetic acid (Gd-DTPA).
- FLT-PET will be obtained within 4 weeks prior to initiation of WBRT and within 2 weeks of the MR Brain. History and physical Examination within 1 week prior to initiation of WBRT.
- Patients will also undergo CBC, comprehensive metabolic panel within 1 week prior to initiation of WBRT.
- Women with childbearing potential will also undergo a serum pregnancy test. See Appendix A for study calendar.

9.1 TREATMENT/INTERVENTION PLAN

9.2 FLT PET

Twenty patients will receive an injection of up to 10 mCi of FLT, followed by FLT PET scan and a blood draw for pharmacokinetic analysis. These twenty patients will also be imaged using MR before and after the administration of gadolinium- diethylenetriamine-pentaacetic acid (Gd-DTPA).

9.2.1 Patient Preparation for FLT PET

No specific dietary restrictions or hydration are required for FLT PET scans, however, patients will be urged to drink plenty of water before and after the PET studies. $[^{18}\text{F}]$ FLT will be prepared under RDRC guidelines by the MSK Radiochemistry Core and assessed for quality control following "good manufacturing practice" criteria. The radiopharmaceutical will immediately be brought to the Nuclear Medicine Radiopharmacy for dispensation in the PET suite. Patients will receive up to 370 MBq (10 mCi) $[^{18}\text{F}]$ -FLT by intravenous infusion.

9.2.2 FLT PET scanning

Following scout view, a low dose CT (80mA) of the brain will be obtained for an anatomic localization and attenuation correction. Following intravenous injection of $[^{18}\text{F}]$ FLT, dynamic PET emission data of the brain will be obtained for up to 60 min to obtain kinetic information on tumor uptake for modeling. Image acquisition shall start immediately after injection using the following sequence: 4 frames of 15 seconds, 4 frames of 30sec, 7 frames of 1-minute, then 10 frames of 5-minutes, i.e. for a full scan duration of 60-minutes. After the 60 minutes dynamic scan, if the patient is capable and willing, an additional 10 minute static acquisition will be acquired at 90 minutes. Dynamic FLT scans will be using standard clinical protocol. Patients may take a break and get off the table, for instance for bathroom break before the additional 10 minute static acquisition.

FLT PET scans will be obtained at baseline (within 4 weeks of WBRT and within 2 week after MR imaging), 7-10 days after WBRT and 10-12 weeks after WBRT.

9.3 MR imaging of the brain

MR imaging before and after the administration of gadolinium-diethylenetriamine-pentaacetic acid (Gd-DTPA) will be obtained within 2 weeks of the PET scan. All baseline imaging scans (FLT-PET and MR Brain) will be obtained within 4 weeks prior to initiation of WBRT. MR imaging will be repeated 10-12 weeks after WBRT. MR imaging during the follow-up scan only will include the T1-Perfusion sequence (DCE) images.

FLT-PET scans are the research scans and MR imaging is considered standard of care.

9.4 Tissue Analysis

For patients who need to undergo a craniotomy for resection of a brain metastases after WBRT, tissue findings (radionecrosis versus viable tumor) will be correlated with radiologic assessment in an exploratory manner.

10.0 EVALUATION DURING TREATMENT/INTERVENTION

10.1 FLT PET

Schema illustrating the duration of FLT scans and the time-point for the blood draw

Intervention	Low dose CT	FLT PET Dynamic Scan for 60 min	FLT PET 10 min Static scan (optional) at 90 min
Low Dose CT [¹⁸ F] FLT injection ¹ Blood Draw ²	X	X X	X

¹ A low-dose CT will be obtained following scout view. After 10 mCi of [¹⁸F] FLT infusion, dynamic FLT scans will be obtained for 60 min. If the patient agrees then static scans will be obtained at 90 min and will last for 10 min.

² One blood draw will be done 60 min (+ 10 min window) after the FLT injection.

10.1.1 Blood Samples during FLT PET

A venous catheter will be placed in a superficial hand or arm vein for administration of the radiopharmaceuticals. A second venous catheter will be placed in the opposite hand or arm for venous blood sampling. If a central venous catheter is present, it will be used for blood sampling or radiopharmaceutical administration, and only a single venous catheter will be placed. All catheters will be removed at the end of the day. One 3 ml venous blood samples will be drawn in a green top tube 60 minutes (+ 10 min window) post-radiopharmaceutical injection from a vein in the arm opposite that used to inject the radiopharmaceutical by research staff. [¹⁸F] radioactivity in the [¹⁸F] FLT blood/plasma sample will be measured by research staff.

10.1.2 FLT PHARMACOKINETIC ANALYSIS

Pharmacokinetic modeling will be done on a voxel-wise basis across the entire segmented tumor. This kinetic modeling algorithm will compute voxel-wise parameter estimates of the compartmental model parameters (K1, k2, k3, and k4) defining tracer exchange between the blood and tumor tissue compartments, as well as V_b, the intravascular blood volume fraction, which will be estimated as a fifth parameter. Parametric maps will then be determined using the estimated proliferation rate constant

(k3) values that, for kinetic FLT PET data, are expected to reflect the spatial distribution of rates of cellular proliferation. A composite parameter, $Ki (K1K3/(k2+k3))$ estimating the irreversible uptake of FLT at equilibrium, will also be evaluated due to its decreased sensitivity to noise and robustness as a measure of irreversible uptake. The information derived from these analyses will not be used for treatment planning, but shall retrospectively be used in the assessment of treatment response. Non-invasive input functions will be obtained from the image data using regions of interest of the superior sagittal sinus. These measurements will be compared with arterial blood activity-concentrations from an image containing the internal carotid artery and will be calibrated using the measurement of a single intravenous blood sample acquired at one post-injection time point.

The utility of static (SUV) versus parametric measures derived from compartmental analysis (i.e., $k3$ and Ki) of ^{18}F -FLT PET represent different approaches. The SUV metric provides a simple measure of the amount of FLT within the defined region of interest at a specific time e.g. 60-minutes post injection. This metric is rapidly obtained and has become the main reporting metric used in FDG PET studies assessing treatment response.

However, when response metrics are sought following aggressive therapies that may significantly impact upon radiotracer delivery to the tumor, such as following high dose radiotherapy or the use of anti-angiogenic agents, compartmental analysis may offer the advantage in that such approaches estimate the rate of tracer entrapment accounting for the radiotracer input function.

To summarize, patient assessment and evaluation will be based on voxel-wise and region of interest (ROI) measurements of the tumor. The tumor will be identified on the CT image of the PET/CT. Standardized uptake values (SUVs) will be estimated from the late time frames of the study. Kinetic rate constants ($K1 - k4$) and the composite parameter Ki will be estimated from the dynamic data. These measurements will be made on both an ROI and voxel-wise basis. Input functions necessary for the kinetic modeling will be made from the either the sagittal sinus or the carotid artery. Measures from both imaging methods (static SUV and parametric measures) will be used in analyses.

10.2 MR Imaging

MR imaging will be done as routine before and after Gd-DTPA.

The time-points of FLTPET and MR Imaging for this study are shown in the study calendar below:

Study Calendar

Tests	Screening (within 4 weeks of WBRT)	7-10 days after WBRT	10-12 weeks after WBRT
MRI Brain*	X		X
FLT-PET*	X	X	X

*MRI and FLT-PET will all be done within 4 weeks prior to initiation of WBRT. MRI will be done within 2 weeks of the FLT-PET scan. MR imaging during the follow-up scan only will also include T1-perfusion images (DCE).

11.0 TOXICITIES/SIDE EFFECTS

The PET scan has no known or expected side-effects. The radiotracer drug, FLT, has been given to patients in other studies and no side effects have been reported. However, in the unlikely event that an adverse reaction (such as an allergic reaction) to the radiopharmaceutical occurs, the results will be documented and reported by the Principal Investigator to the Institutional Review Board Chairman and IND Committee. Patients could experience claustrophobia due to the MRI scanner. If they have difficulty tolerating the study, it will be stopped. THE PET/CT scanner is not confining like the MRI scanner. Additionally, patients are advised not to become pregnant or father a baby while on this study. Women should also not breastfeed the baby. Patients will be required to use birth control while on study. Very rarely, patients can develop nephrogenic systemic fibrosis which has been correlated with the use of gadolinium based contrast material used during the MRI scans.

Placement of a catheter for infusion of ¹⁸F-FLT and blood samples may cause pain, bruising, itching, infections and venous scarring. Standard medical care will be used to minimize these risks.

11.1 PET SCANNING

Potential risks to the patient are small and present more of an inconvenience (multiple scans on consecutive days). The PET has a large bore to accommodate the whole body and the environment is much less confining than the head cage of a MR tomograph.

11.2 DOSIMETRY

Table 1. F18-Fluorothymidine (FLT) Patient Dosimetry							
Absorbed Dose							
1 FLT PET-CT scans							
		0.9		CT rads		3*0.9	
		F18-FLT²		10 mCi F18-FLT		3 FLT PET-CT scans	
Target Organ		rad/mCi	rad/10 mCi	rad	-	-	rad
Adrenals		0.0766	0.77	1.67			5.00

Bone Surfaces	0.0585	0.58	1.48		4.45
Brain	0.0125	0.13	1.03		3.08
Breasts	0.0310	0.31	1.21		3.63
Gall Bladder Wall	0.0625	0.63	1.53		4.58
Heart Wall	0.0618	0.62	1.52		4.55
Kidneys	0.132	1.32	2.22		6.65
Large Intestine - Lower Wall	0.0168	0.17	1.07		3.21
Large Intestine - Upper Wall	0.0459	0.46	1.36		4.08
Lens of Eye	0.0389	0.39	1.29		3.87
Liver	0.1680	1.68	2.58		7.74
Lungs	0.0374	0.37	1.27		3.82
Muscle / Other tissue	0.0622	0.62	1.52		4.56
Pancreas	0.0851	0.85	1.75		5.25
Red Marrow	0.0888	0.89	1.79		5.36
Skin	0.0164	0.16	1.06		3.19
Small Intestine	0.0525	0.53	1.43		4.28
Stomach Wall	0.0522	0.52	1.42		4.27
Testes	0.0488	0.49	1.39		4.17
Thyroid	0.0385	0.38	1.28		3.85
Total Body	0.0466	0.47	1.37		4.10
Urinary Bladder Wall					
45-min Voiding Interval	0.0297	0.30	1.20		3.59
1-hr Voiding Interval	0.0396	0.40	1.30		3.89
1.5-hr Voiding Interval	0.0593	0.59	1.49		4.48
2-hr Voiding Interval	0.0791	0.79	1.69		5.07

12.0 CRITERIA FOR THERAPEUTIC RESPONSE/OUTCOME ASSESSMENT

MR Imaging

Response assessment for MR Imaging of the brain during the follow-up period will be done by using Macdonald Criteria [25] as follows:

12.1 Measurable lesion

In the presence of multifocal disease, up to five bi-dimensionally measurable enhancing mass lesions will be followed for objective response. The bidimensional perpendicular measurements for each lesion should always be assessed in the same plane of axis (axial, coronal, sagittal or other). The largest perpendicular diameters of enhancement for each mass lesion will be recorded. Any and all remaining enhancing lesions will be followed as a single site and classified as an evaluable lesion. Objective response of the measurable lesion will be assessed by comparison of the changes in the product of the largest perpendicular measurements of the lesion at each visit. Comparisons of objective assessments for a measurable lesions(s) excluding progressive disease, are based upon major changes in tumor size on the Gd-MRI scan compared to the baseline scan. Determination of progressive disease is based upon comparison to the previous scan with the smallest measurements. Comparisons should always be made with measurements assessed in the same plane of axis (axial, coronal, sagittal or other).

12.2 Evaluable lesion(s)

For multifocal disease, all remaining enhancing tumor lesions, beyond the 5 measurable or any lesions that cannot be measured, will be followed as a single site and classified as an evaluable lesion. For an evaluable lesion(s), comparison of assessments for response designation will be assessed based upon major changes in tumor size on Gd-MRI scan. Comparisons of assessments for evaluable lesions(s) excluding progressive disease, are based upon major changes in tumor size on Gd-MRI scan compared to the baseline scan. Determination of progressive disease is based upon comparison to the previous scan with the smallest amount of evaluable tumor. Tumors may be classified as complete response (CR), partial response (PR), stable disease (SD), or progressive disease (PD).

A complete response will always be disappearance of all enhancing tumor. Progressive disease will always include any new enhancing tumor.

12.3 Criteria for current objective status

At each tumor assessment visit the current objective status is determined. This takes into account measurable and evaluable lesion(s). Comparisons of assessments for measurable and evaluable lesions, excluding progressive disease, are based upon major changes in tumor size on Gd-MRI scan compared to the baseline scan. The assessment is adapted from Macdonald et al. Determination of progressive disease is based upon comparison to the previous scan with the smallest measurements. Scan changes are emphasized, but are interpreted in light of steroid use and to a lesser extent, neurological findings. Categories of overall response include:

Complete response (CR): Disappearance of all enhancing tumor on consecutive MRI scans at least one month apart, off steroids and neurologically stable or improved. No new lesions may arise.

Partial response (PR): Greater than or equal to a 50% reduction (< 100%) in the sum of the products of the largest perpendicular diameters of contrast enhancement for measurable lesions and if an evaluable lesion(s) is present at baseline, no worsening for an evaluable lesion(s) on consecutive Gd-MRI scans at least one month apart, steroids stable for 72 hours prior to each scan at the same dose administered at the time of the previous scan or at a reduced dose, and neurologically stable or improved. No new lesions may arise.

Progressive disease (PD): Greater than or equal to a 25% increase in size of the product of the largest perpendicular diameters of contrast enhancement for any measurable lesions or if an evaluable(s) lesion is present at baseline, worsening for an evaluable lesion(s) or any new tumor on Gd-MRI scans or greater than or equal to 25% increase in the unidimensional measurement of the any lesion in an additional plane of axis, steroids are stable for 72 hours prior to each scan at the same dose administered at the time of the previous scan or at an increased dose, with or without neurological progression. The following will also apply:

Unknown (UNK): If any measurable or evaluable lesions have not been assessed or the assessment was made using a technically inferior method compared to baseline, the current objective status is “unknown”, even if the bulk of disease was evaluated. An exception would be if the objective status is PD because either a new lesion was detected, evaluable disease clearly worsened or the remaining lesions classify for a PD even without the lesions which were not assessed, i.e. the sum of all lesions which can still be measured show an increase of more than 25% over the smallest sum of all measurable lesions which were present at baseline.

Stable disease (SD): All other situations.

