12.4 Best response

The best response for each patient is determined from the sequence of objective statuses. The terminology for the five categories of objective status is identical to those that describe best response.

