12.4.1 Determination of best response

The best response for each patient is determined from the sequence of objective statuses according to the following rules:

CR = at least two determinations of CR a minimum of 4 weeks apart before progression, preceded by lower statuses, or preceded, separated or followed by unknown statuses.

PR = at least two determinations of PR or better a minimum of 4 weeks apart before progression (but not qualifying for CR), preceded by lower statuses, or preceded, separated or followed by UNK statuses.

SD = at least one determination of stable disease or better

PD = a determination of progression in one of the first two assessments

UNK = the status is UNK only if all assessments before progression are UNK.

If there is a defined objective that includes the assessment/measurement of therapeutic response to the defined treatment intervention, then detailed description of the measure, methods to be used (e.g., scales and/or definitions to assess response) and the criteria to determine each level of therapeutic response should be included.

FLT-PET

Response assessment for FLT-PET will be as follows:

SUV max and average (42% threshold) for brain lesions will be measured (for FLT using summed images 45-60min). In addition, we will explore other measures such as metabolic tumor volume. For comparison, activity will also be measured in remote normal cortex and white matter. Tumor - to-normal ratios will be computed. Treatment induced changes in these parameters will be expressed as % decrease in radiotracer uptake. Tentatively, a decline by 25% [26] will be considered significant.

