14.0 BIOSTATISTICS

This is a small pilot study involving 20 patients with brain metastases from breast cancer. The first cohort will include the first ten patients that are enrolled to a separate but simultaneous phase I study evaluating patients receiving concurrent sorafenib + whole brain radiotherapy (WBXRT). *The goal of the phase I study is to determine the MTD of sorafenib in breast cancer patients with brain metastases receiving WBRT.* Ten additional patients who do not enter the parallel phase I trial and receive WBXRT without sorafenib, will be consented to this imaging study. Both cohorts have the same eligibility criteria.

The first ten patients recruited into the Phase I trial of sorafenib + whole brain radiotherapy will have to agree to consent to the FLT-PET imaging study. The cohort receiving WBRT alone will be recruited independently.

The primary objective of this study is to examine radiographic response to WBRT by two modalities: FLT-PET and MRI. MRI is considered standard of care and response assessments are recorded as

CR, PR, PD, SD, and unknown (see section 12.0). FLT-PET response assessments will be recorded as SUV-MAX and a decline by 25% is considered as significant (see Section 12.0). MRI measurements will be recorded at baseline and 10 to 12 weeks post WBRT. FLT-PET measurements will be recorded at baseline, 10 days post WBXRT, and 10-12 weeks post WBXRT.

This is a small pilot study and as such, we are limited in the scope of our analyses by sample size. Data from each modality will be examined descriptively and graphically at baseline and over the course of treatment. Specifically, the distribution of response at baseline and the 10-12 week post WBXRT timepoint as assessed by MRI and FLT-PET will be examined. The median, mean, min and max of SUV max for FLT-PET will be summarized at each timepoint. Significant or nonsignificant change in SUV from baseline to the 10-12 weeks post WBRT timepoint (decline by 25%) will also be calculated and the frequency of patients with significant change will be calculated. These descriptive analyses will be done for each cohort separately. Because FLT-PET can be used to assess early treatment response, SUV values and significant SUV change from baseline to 10 days post WBRT will be examined descriptively.

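### As written, Section 12.3 codes complete disappearance at the 10-12 week MRI as stable disease, and Section 14 does not say which response status it tabulates

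*Combined protocol and SAP*

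**What the plan says.** Section 12.3 defines a visit-level status: "At each tumor assessment visit the current objective status is determined". Its categories are as follows.

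- CR: "Disappearance of all enhancing tumor on consecutive MRI scans at least one month apart, off steroids and neurologically stable or improved", with no new lesions.
- PR: "Greater than or equal to a 50% reduction (< 100%) in the sum of the products" of diameters. A consecutive-scan clause follows the condition on evaluable lesions, along with steroid and neurological conditions.
- Unknown: only where lesions were not assessed or an inferior technique was used.
- The rest: "Stable disease (SD): All other situations".

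Section 12.2 adds: "A complete response will always be disappearance of all enhancing tumor".

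Section 12.4 treats best response as a separate quantity: "The best response for each patient is determined from the sequence of objective statuses". Section 12.4.1 puts confirmation there: "PR = at least two determinations of PR or better a minimum of 4 weeks apart before progression", with a parallel two-determination rule for CR.

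Section 14 states: "MRI measurements will be recorded at baseline and 10 to 12 weeks post WBRT". It tabulates the response distribution at 10-12 weeks and refers to Section 12.0 as a whole for the categories. It then compares FLT-PET with MRI across CR+PR versus PD+SD, using boxplots and McNemar's test. It names no timepoint and no confirmation rule for that comparison. FLT response is a 25% fall in SUV between single scans and needs no confirmation (Sections 12.0 and 14).

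**The concern.** A status assigned at one visit cannot satisfy a definition that needs two scans. At the first post-treatment MRI the CR category is therefore unreachable. The upper limit on PR stops a complete disappearance from falling back to PR, so it drops to SD. The order of outcomes is then inverted: the best possible MRI result can rank below a partial one.

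MRI response is half of the first primary objective. The same coding would feed the 10-12 week table, the boxplots by MRI category and, if the comparison uses that timepoint, the CR+PR versus PD+SD split. Section 14 does not settle which status applies, so two analysts could build different tables from the same scans.

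**Working it through.** The plan has no figure of its own to reproduce here. The check applies the stated rule to one post-treatment scan and then illustrates the size.

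**1. Number of scans.** Section 4.3, the calendar in Section 10.2 and Appendix A show MRI at baseline and at 10-12 weeks, with none at 7-10 days. At 10-12 weeks there is one post-treatment MRI.

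**2. Applying Section 12.3 to that scan.** The PR sentence has two readings. The consecutive-scan clause may attach only to the evaluable-lesion condition (narrow) or to the whole criterion (broad). Assume no new lesions, steroid and neurological conditions met, and no evaluable lesions beyond the measured ones.

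| Reduction from baseline | Narrow PR reading | Broad PR reading |
|---|---|---|
| 100% | SD | SD |
| 80% | PR | SD |
| 50% | PR | SD |
| 40% | SD | SD |

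Complete disappearance is SD under both readings. It is not CR (one scan), not PR (100% is excluded), not PD, and not unknown (all lesions were assessed by an adequate method). With a second qualifying clear scan it becomes CR.

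**3. Set against Section 12.4.1.** Best-response CR needs two CR determinations. If each determination already needs two consecutive clear scans and is made at the second of them, best-response CR needs three clear scans. Confirmation has been applied twice.

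**4. A gap that confirmation does not close.** A patient with complete disappearance who is still on steroids fails CR and is also barred from PR by the upper limit. That patient is SD however many clear scans follow.

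**5. When a confirming scan could come.** The tabulated MRI is at day 70-84 after WBRT.
- If three-monthly scans count from that MRI, the next is 91 ± 7 = 84-98 days later.
- If they count from WBRT, the first (day 84-98) is only 0-28 days later, which is short of a month. The next (day 175-189) is 175 − 84 = 91 to 189 − 70 = 119 days later.

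The first scheduled scan that could confirm is thus 84-119 days after the one being tabulated.

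**6. Illustrative size, narrow PR reading.** Section 14 gives N = 20 and an MRI response rate of 65-70%: 0.65 × 20 = 13 and 0.70 × 20 = 14. The documents give no CR rate, so let k complete disappearances be coded SD, with k = 1-4 assumed. Suppose also 20 evaluable pairs, that these k patients are FLT responders, and that the modalities otherwise agree. Then all k discordant pairs point one way, and exact two-sided McNemar p = min(1, 2 × 0.5^k).

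| k | Recorded MRI responders of 20 | Exact McNemar p |
|---|---|---|
| 1 | 12-13 | 1.0 |
| 2 | 11-12 | 0.5 |
| 3 | 10-11 | 0.25 |
| 4 | 9-10 | 0.125 |

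Each recoded patient moves the response proportion by 1/20 = 5 percentage points overall, or 1/10 = 10 points within a cohort.

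**The case against.** The strongest reply is that the intended meaning can be recovered. Section 12.3 speaks of each visit, Section 12.4 builds best response from a sequence of visit statuses, Section 12.4.1 holds the two-determination rule, and Section 14 names one timepoint for the response distribution. Together these point to a single-visit status, confirmed later for best response only. That is right about intent, but it does not remove the defect: the operative CR definition says otherwise, and Section 14 does not override it.

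Several stronger readings are tempting, and the documents do not support them.

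- *Section 12.2 contradicts Section 12.3.* Its sentence on CR can be read as a necessary condition to which 12.3 adds others. The real overlap is between 12.3 and 12.4.1.
- *The plan has no means of upgrading a response later.* For best response it has: 12.4.1 allows CR or PR to be preceded by lower statuses, and MRI continues every three months in the first year. What is missing is a rule for revising the 10-12 week status or a statement that Section 14 uses best response.
- *No patient could be recorded as a responder at 10-12 weeks.* That 0/20 result is a limiting case. It needs the broad PR reading and no later reassignment.
- *The coding always inflates disagreement between modalities.* It does so only for FLT responders. For a patient without a 25% SUV fall, recoding to SD creates agreement.

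The stakes are also limited: this is a descriptive pilot, and the FLT results do not affect patient management.

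**Conclusion.** The point holds as a coding error in a descriptive pilot. Followed as written, Section 12.3 gives the wrong category to complete disappearance at the 10-12 week MRI, and Section 14 leaves open which status is analysed. The error can only lower recorded MRI response at that timepoint, and it affects the best responders.

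Its size cannot be established from the documents. The range of 9-13/20 against 13-14/20 rests on an assumed 1-4 complete disappearances, the narrow PR reading, no later reassignment, and the plan's 65-70% rate taken as the true single-visit rate. Some of those patients might miss CR anyway through the steroid condition, and the share is unknown. A reader might infer that McNemar's test would be seriously distorted. In this range p never falls below 0.125, so the visible effect is on the table, the boxplots and the group split. Table 2's PFS figures do not give a reliable estimate of how many responses would go unconfirmed: they carry no units and do not describe MRI responders.

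It should be fixed before analysis.

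**What to change.** 1. In Section 12.3, define CR and PR for the single visit against baseline, keeping the other conditions. Leave the confirmation requirement in Section 12.4.1 only.
2. In Section 14, state that the 10-12 week table, the boxplots and the FLT comparison use the single-visit 12.3 status, and report confirmed best response under 12.4.1 in a separate table.
3. State which category applies when enhancement has fully disappeared but another CR condition fails, so that the patient does not become SD merely because PR stops short of 100%.

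The cost is a few sentences in Sections 12.3 and 14, with no extra scan, visit, patient or data item. The drawback is that unconfirmed response is slightly more generous; the separate confirmed table offsets it. Basing the main table on 12.4.1 best response would also be coherent, but neither CR nor PR can be reached there from one post-treatment scan, so the table would have to wait for later MRIs. Whichever is chosen, Section 14 must name it.
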